9.0 DURATION OF STUDY

The study includes hysterectomy with identification of sentinel lymph nodes on consecutive LREC and HREC patients.

The patient may withdraw from the protocol at any time prior to surgery or at any time until retrieval of postoperative data until 2 year after surgery.

The study was initiated at Lund university hospital (From january 2019) with potential later inclusion of a second or more investigating centers which will motivate a revision of the study protocol related estimated time for enrollment of patients and for accreditation of the second centre and surgeons. The annual volume of endometrial cancer patients in Lund is close to 200 with an estimated 85% suitable for minimally invasive surgery and inclusion in the study.

Related statistical analyses below a total of 362 patients will need to be included with an interim analysis after 150 patients.

10 STUDY MONITORING AND REPORTING PROCEDURES

ADVERSE EVENT REPORTING

The study protocol has been revised related principles study monitoring and for reporting adverse events to the principal investigating center after inclusion of the second center.

Definitions

An adverse event (AE) is any new medical problem or exacerbation of an existing problem experienced by a subject enrolled in the study, whether or not it is considered drug-related by the investigator.

This study will utilize the Adverse Events Logs (Tables 10.1-5). Any SAE will be reported to the study coordinator ([contact]) using the SAE log. (appendix 1).

Adverse events related to the study drug (ICG).

All adverse events occurring from the first dose of study drug until hospital discharge (whether or not attributed to the study drug) will be reported on the Adverse Event Log. In addition, any adverse event reported by the subject to the investigator after discharge and determined to be reasonably associated with the study drug should also be captured and followed until resolution.

Adverse events related to the sentinel node procedure as such (excluding AE related the study drug, ICG)

All intraoperative events related to the SLN procedure will be reported on the adverse events log.

Adverse events related the surgical procedure (excluding the SLN part) including AE until 30 postoperative days.

All adverse events will be reported on the adverse events log.

Serious adverse event (SAE):

An adverse event that results in one or more of the following:

- Any death occurring prior to the postoperative outpatient evaluation 30 days postoperatively.
- Any life-threatening event until and including 30 postoperative days.
- Any medical event requiring inpatient hospitalization or prolongation of existing hospitalization beyond five postoperative days

NOTE: Hospitalizations that are not considered SAE are:

- Hospitalization planned prior to first administration of study drug
- Hospitalization for elective treatment of a pre-existing condition unrelated to the study medication
- Hospitalization due to social / practical reasons such as an untimely coordination with local community home care services.

Attribution: Attribution is the determination of whether an adverse event is related to a medical treatment or procedure. The categories of attribution are:

Definite: The adverse event is clearly related to the study drug

Probable: The adverse event is likely related to the study drug.

Possible: The adverse event may be related to the study drug.

Unlikely: The adverse event is doubtfully related to the study drug.

Unrelated: The adverse event is clearly NOT related to the study drug.

Unexpected Adverse Event: An unexpected adverse event is an event not mentioned in the package insert/ manufacturer's instructions or the specificity or severity of which is not consistent with the package insert/ manufacturer's instructions.

The grading described beneath and the attribution described above will be used for categorization of unexpected adverse events.

Participating Center Reporting Responsibilities

Reporting to the study coordinator

Any SAE's must be reported to study Coordinator at Lund University Hospital within 3 working days of discovery of the incident, using the study-specific SAE Form.

Email: [contact]

The lead and local principal investigators and the study coordinator shall conduct continuous review of data and patient safety for a monthly summary of the included number of patients, patient safety and significant AE's described in the protocol.

All SAE's potentially associated with the study drug, the sentinel node procedure as such or deaths shall be evaluated by a

Reporting to the IRB:

Each participating center will report adverse events to their IRB per local guidelines.

Coordinating Center Reporting Responsibilities

Reporting to the study coordinator, Lund University Hospital

Same criteria as above.

Reporting to the IRB:

Same criteria as above.

The Study Coordinator will distribute reports which are serious, unexpected and associated with the study intervention (possibly, probably or definitely) to all participating investigators. Copies of all serious adverse event reports will be kept on file the department of Obstetrics and Gynecology, Lund University Hospital.

The study coordinator will also report all individual SAE's related to study drug, the sentinel node procedure as such, are life threatening or resulting in death (defined above and in table 10.6) to the Safety Monitoring Committee (SMC) for clinical studies at Skåne University Hospital for an independent evaluation.

At any time during the conduct of the trial, if it is the opinion of the investigators that the risks (or benefits) to the patient warrant early closure of the study, this recommendation should be made in writing to the SMC. Alternatively, the SMC may initiate suspension or early closure of the study based on its review of the investigator reports.

Study Monitoring / study accrual oversight

The study principal investigator, any local principal investigator and study coordinator will conduct meetings (teleconferenced) every 6 months to discuss the protocol. The Study-PI and local-PI can call a meeting to convene at additional times if deemed necessary, for example following statistical review at the interim period if stopping the study for either achieved goals or futility. Apart from the monitoring described below, the number of node positive patients and potential false negative SLN's will be monitored continuously by e-mail to the study coordinator by the use of the study number assigned to each patient.

In case of identified inconsistencies or missing data, additional source documents (identified only by unique patient number) will be requested from the site to resolve ongoing inconsistencies.

The principal investigator and/or the study coordinator will, if deemed necessary by the principal or second participating center perform audits of informed consents and subject eligibility.

Data Management

Preoperative, intraoperative and postoperative data from each surgery will be recorded on the standardized study sheets. These study sheets will be made available to each study site. Each study site will be allocated a study number which will serve as the prefix to the case number. For example, Lund university Hospital will be allocated the prefix "Lu" and the first study patient will have the study number "LU-001. Each investigating center will hold a record with the full identification of patients whereas data otherwise should only identify the patient by the study number (see above).

Staff at the individual centers will be responsible for completing the data collection sheet for each patient and all data will continuously be entered into a common secured password

secured database using the designated study numbers. Upon interim analysis the full data will be monitored by the study coordinator, the principal investigator, local principal investigator and study statistician.

Separate analysis of patient data from individual sites can only be performed with the written permission of the study principal investigator.

Early Study Closure

Death will be reported according to section 10.1 above and per local IRB reporting guidelines. The SMC will review all reported deaths monthly. Early closure of the study will be based on judgement of the SMC.

The study will be stopped for futility reasons as described under the statistics section.

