1. OBJECTIVES

To estimate the efficacy of a pelvic sentinel lymph node (SLN) concept for diagnose of pelvic nodal metastases in patients with low and- high risk endometrial cancer using a cervical injection of Indocyanine Green (ICG) as tracer and robot assisted near infrared (NIR) imaging using an anatomically based surgical algorithm and definition of sentinel lymph nodes. The observed percentage of metastatic sentinel nodes will be evaluated from a non-inferiority perspective based on an assumed percentage of pelvic nodal metastases estimated from final detailed histological data (myometrial invasion, cervical stromal invasion, histological type and grade)

To estimate the proportion of low- and high risk endometrial cancer patients suitable for the SLN concept in conjunction with robotic surgery

To estimate time for the SLN procedure and intraoperative complications associated with detection of SLN as such (study intervention) and postoperative adverse events until 30 days as well as objective measurement of leg volume and lymphedema symptoms by the use of a validated questionnaire up and until two years after surgery.

To estimate health economy aspects of the SLN concept.

To estimate complications associated with ICG as tracer

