5.0 TREATMENT PLAN/ FOLLOW UP

Patients with metastatic SLN's shall be planned for a restaging procedure including pelvic and paraaortic lymph nodes.

Importantly, all intraoperative adverse events associated with the study intervention and the study drug (ICG) will be recorded in protocol as the separate time used for the detection and removal on SLN's. Likewise, complications associated with the restaging procedure shall be included on an intention to treat basis.(additional CRF)

All adverse events, including postoperative until 30 days, shall be evaluated whether attributable to the study intervention or not.

Measurement of leg volume as an objective parameter of lymphedema shall be performed at one and two year follow up and at symptoms.

Symptoms associated with lymphedema shall be evaluated by a designated QoL Form used before surgery, after surgery at symptoms, and at one and two years after surgery. A symptoms score shall be used at every follow up.

NOTE: Surgeons' skill and adherence to protocol will be verified as described above.

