8.0 EVALUATION CRITERIA

- All patients who are injected with ICG with at least one SLN type1-2, macro and SLN anatomy and not converted to open surgery before detection and removal of SLN's will be included for evaluation of detection rate of metastatic pelvic nodes all together and with evaluation of ICG defined (SLN type1-2) separately.
- Time used for the study intervention (Injection and reinjection of ICG and detection / removal of SLN's) shall be separately recorded
- All patients included, regardless of conversion to open surgery and mapping of ICG will be included in the overall evaluation of feasibility and safety.
- Intraoperative adverse associated with the detection and removal of SLN will be evaluated and reported separately on all patients who have at least one SLN removed regardless of type, i.e all patients in whom SLN were removed separately.
- Postoperative complications until 30 days after surgery will be reported.

-Perioperative and postoperative complications related restaging will be evaluated on an intention to treat basis.

-An increase in leg volume of 10 % or more compared with the preoperative volume will be defined as a new onset of lymphedema.

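### The five-grade attribution scale is worded only for the study drug, although Section 5 and the rule for informing investigators need attribution to the whole study intervention

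*Combined protocol and SAP*

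**What the plan says.** Section 10 (Definitions) opens its paragraph on attribution broadly: "Attribution is the determination of whether an adverse event is related to a medical treatment or procedure". The five categories that follow are narrower. The first is "Definite: The adverse event is clearly related to the study drug" and the last is "Unrelated: The adverse event is clearly NOT related to the study drug". The three between them (probable, possible, unlikely) have the same object. The identical list is repeated in the appendices with the serious adverse event (SAE) log.

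The study intervention is described more widely elsewhere. Section 8 itemises it: "Time used for the study intervention (Injection and reinjection of ICG and detection / removal of SLN's". Section 1 attaches the label to SLN detection: "intraoperative complications associated with detection of SLN as such (study intervention".

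Two rules depend on attribution to that intervention:
- Section 5: "All adverse events, including postoperative until 30 days, shall be evaluated whether attributable to the study intervention or not".
- Section 10 (Coordinating Center Reporting Responsibilities): the study coordinator circulates reports that are "serious, unexpected and associated with the study intervention (possibly, probably or definitely) to all participating investigators".

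Expectedness, which is also a condition of the second rule, is defined as follows: "An unexpected adverse event is an event not mentioned in the package insert/ manufacturer's instructions".

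**The concern.** The scale and the rules that use it refer to different things. The scale asks whether ICG caused the event. The rules ask whether the intervention did, and the intervention includes a surgical dissection. An investigator who follows the printed definitions must put a nerve or vessel injury from SLN removal in the lowest category, because the dye plainly did not cause it.

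Two things are at stake. First, a serious procedure-related event can fail the relatedness condition for circulation to the participating investigators. Second, the judgement that Section 5 requires for events up to 30 days has no defined scale, so different assessors may record it differently or not at all. Section 11 presents SLN as a replacement for full lymphadenectomy in high-risk patients and as an added procedure in low-risk patients, so harm due to SLN removal matters to how the results will be read. Causality judgements that are not recorded at the time are hard to reconstruct later.

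**Working it through.** No arithmetic applies. The check sets the provisions side by side and follows two kinds of event through them.

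**What each provision refers to**

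| Provision | Object of the judgement | Graded? |
|---|---|---|
| Section 10, lead-in to attribution | A treatment or a procedure | No |
| Section 10, five categories (repeated with the SAE log) | Study drug only | Yes, five grades |
| Section 5, events to 30 days | Study intervention | No, attributable or not |
| Section 10, circulation to investigators | Study intervention | Yes, three of the five grades |
| Section 8, content of the intervention | ICG injection and reinjection plus SLN detection and removal | Not applicable |
| Section 10, SAEs sent to the Safety Monitoring Committee (SMC) | Study drug, or SLN procedure, or life-threatening or fatal | No |

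The second row conflicts with the first, third and fourth. The circulation rule borrows grade names that are defined only for ICG and applies them to something larger.

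**Event A: a serious injury during SLN dissection**
- Capture: it is recorded. Section 10 puts intraoperative SLN events on the adverse event log, Table 10.2 is reserved for them, Appendix 2 has a field for complications during SLN removal, and the SAE log has its own row for the SLN procedure.
- Analysis: Section 8 reports these events separately for all patients with at least one SLN removed, without needing a grade.
- SMC: reached, because that rule names the SLN procedure.
- Circulation to investigators: uncertain. On the printed scale the grade is unrelated, so the possible/probable/definite condition fails. If the rule's own object (the intervention) governs, the condition can be met, but no definition of the grades then exists.

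**Event B: a postoperative event within 30 days that may be due to SLN removal**
- Section 10 collects only intraoperative events under its SLN heading. Events to 30 days fall under a heading for surgery that excludes the SLN part.
- Table 10.5 is not divided by procedure, and the SAE log has one general row for postoperative events.
- The attribution column is therefore the only link on these logs between the event and SLN removal, and the defined scale for that column asks about ICG.
- The specimen rows for Tables 10.4 and 10.5 enter attribution as *No*. That is not one of the five grades, and it does not say whether ICG or the procedure is meant.

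**Expectedness.** The definition rests on the package insert or the manufacturer's instructions. The drug information in Sections 4.0/5.0 describes ICG adverse effects as exclusively allergic. On that basis practically every surgical injury counts as unexpected. The condition does not screen these events out, but it does not separate foreseeable surgical complications from surprising ones either.

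**The case against.** The strongest reply is that the reporting system is wider than the scale, and most of that reply stands. Every SAE goes to the coordinator within 3 working days whatever its attribution. SAEs related to the SLN procedure, and those that are life-threatening or fatal, go to the SMC, which can suspend or close the study. The lead and local investigators review safety continuously, with a monthly summary. The SAE log separates ICG, the SLN procedure and the remaining surgery. Appendix 3 records lymphocysts, lymphoedema and nerve effects, although it does not establish their cause.

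A reader might infer that harm from SLN dissection can be attributed only to the drug, that it escapes safety alerts altogether and that it drops out of the safety estimate. The documents do not support this. The SAE log and the SMC rule name the procedure, and intraoperative SLN events are counted by operative phase. Nor is an SLN-attributed count of postoperative complications a stated objective: Section 1 ties SLN complications to the intraoperative period and lists postoperative events without that link. The requirement comes from Section 5. It would also be wrong to say that the expectedness definition excludes surgical injuries, since it tends to include them.

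It can further be argued that the circulation rule says intervention, not drug, and so already covers SLN harm. That is a reasonable reading of its intent. It does not supply the missing grades, and it leaves the coordinator to choose between that rule and the printed definitions. Likewise, the *No* entries in Table 10.5 could be the yes/no judgement that Section 5 asks for, but the form does not say so.

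**Conclusion.** The concern holds in a limited form. The only defined causality scale covers ICG alone and conflicts with its own lead-in, with Section 5 and with the circulation rule. Two consequences follow if the scale is applied as printed: a serious SLN-dissection event is graded unrelated and may not be circulated to all investigators, and 30-day postoperative events (Table 10.5 and the postoperative row of the SAE log) cannot be attributed to the SLN procedure on a defined scale, as Section 5 requires. Intraoperative SLN reporting and the SMC route are unaffected.

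The size cannot be calculated. The documents give no rate of SLN-related events, and no lost event can be shown. The conclusion assumes that assessors follow the printed category definitions; those who read the grades as referring to the intervention would avoid the wrong grade, but without a common definition. The change should be made because it is cheap and because the present text gives a wrong rating when followed literally.

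**What to change.** - Reword the five categories in Section 10, and their copy with the SAE log, so that each event is rated twice: once for ICG and once for the SLN procedure.
- Carry both ratings in Tables 10.1 to 10.5 and in the SAE log, including its postoperative row. Replace the specimen *No* entries with defined grades.
- State that the rule for circulating reports to investigators is met when either rating is possible, probable or definite.
- Give expectedness a reference for procedure events, for example a list of recognised complications fixed in the protocol, and keep the package insert for ICG events only.

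The cost is a wording change in Section 10 and the appendix, one extra column on the logs and slightly more recording work. No extra staff are needed, and neither the treatment nor the efficacy analysis changes.

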Grade IV	Life-threatening complication (including CNS complications)* requiring IC/ICU-management - IVa single organ dysfunction (including dialysis) - IVb multiorgan dysfunction
Grade V	Death of a patient

11. STATISTICAL CONSIDERATIONS

This study is designed to evaluate the ability of the sentinel node (SLN) technique to determine pelvic lymph node metastases in patients with low- and high risk endometrial cancer as a replacement for a full lymphadenectomy in the latter and as an increased diagnostic procedure in the former.

The main statistical endpoint will be to evaluate the SLN concept by a non-inferiority analysis, i.e its ability to detect nodal metastatic disease compared with an estimated proportion which with a 50/50% distribution of LREC and HREC result in approximately 12% of women having pelvic nodal metastases. This will be tested against 8% metastatic SLN's as null-hypothesis. With a one-sided analysis (Alfa-error of 5% and 80% power) 362 patients need to be included with a planned interim analysis after 150 patients.

If then 22 or more patients are identified as SLN-node positive the null-hypothesis will be rejected and the study closed. If 12 or fewer patients are identified as SLN node positive the study will be closed for futility. If the number of node positive patients is between 12 and 21 the study will continue to enroll a total of 362 patients (Fleming, 1982).

The measurements of leg volume/lymphedema are based on an estimated risk for lymphedema following SLN only of 1% (null hypothesis) compared with the group of SLN positive (HREC and LREC) with an estimated risk of 4% (20% node positive with 20% risk of lymphedema) with an estimated distribution between group of 88% SLN negative and 12% SLN positive with restaging (SLN+LND). A total of 169 patients need to be included with a planned interim analysis after 65 patients. If 3 or more patients in the SLN+LND group have lymphedema the null hypothesis can be rejected provided no more than one patient in the SLN only group have developed lymphedema.

BIBLIOGRAPHY

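### The replacement claim concerns high-risk women only, but the sole decision rule pools both risk groups, so a pooled rejection does not by itself support it

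*Combined protocol and SAP*

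**What the plan says.** Section 11 states two aims. SLN is to serve "as a replacement for a full lymphadenectomy in the latter and as an increased diagnostic procedure in the former". The planning rate is one figure for both groups, "which with a 50/50% distribution of LREC and HREC result in approximately 12% of women having pelvic nodal metastases". The test is also pooled: "This will be tested against 8% metastatic SLN's as null-hypothesis". The size follows: "With a one-sided analysis (Alfa-error of 5% and 80% power) 362 patients need to be included".

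The interim rules at 150 women use the same pooled count: "If then 22 or more patients are identified as SLN-node positive the null-hypothesis will be rejected and the study closed", and "If 12 or fewer patients are identified as SLN node positive the study will be closed for futility". Otherwise enrolment continues to 362. No final critical count is printed. Section 11 gives no HREC hypothesis, no separate HREC and LREC rates and no stratified test.

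Elsewhere:

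- Section 8.0 evaluates detection in all evaluable women as one group; the only breakdown it names is by type of SLN.
- Section 1 describes a comparison with a metastasis percentage estimated from each tumour's final histology. Section 11 does not carry this into the test.
- Section 4.0/5.0 and the surgical form (Appendix 2) plan SLN without full lymphadenectomy in HREC unless nodes are suspect or mapping fails. The overview study plan lists complete pelvic lymphadenectomy without limiting it to a group.

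**The concern.** Replacing lymphadenectomy in HREC is a non-inferiority question: does SLN find nearly all the disease that the larger operation would find? In LREC the procedure is an addition, and a positive there says nothing about misses in HREC. In a pooled count the two are interchangeable: one extra LREC positive cancels one missed HREC positive.

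A pooled success, possibly at 150 women of whom about 75 are HREC, would close the study and could be read as support for omitting lymphadenectomy in HREC. That inference does not follow from the test. If HREC women have SLN only, most misses would not be observed, so the count carries the whole argument.

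**Working it through.** **Inputs from Section 11.** Null 8%, expected 12%, interim n = 150 with limits 12 and 22, total 362, mix 50/50. I count exactly 12 positives as futility.

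**Assumptions.** (a) The final cut-off is 38, the smallest count that keeps the one-sided error at or below 5%. (b) Each group supplies half the women at each stage: 75 + 75, then 106 + 106 (362 − 150 = 212). (c) The HREC rate h and LREC rate l are not given; any pair with (h + l)/2 = 12% fits, and I use 24/0 to 16/8.

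**Formula.** X1 = Bin(75, pH) + Bin(75, pL) and X2 = Bin(106, pH) + Bin(106, pL). The pass probability is P(X1 ≥ 22) + Σ over x = 13 to 21 of P(X1 = x) · P(X2 ≥ 38 − x).

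**Step 1: the plan's own figure.** With one common rate, this gives an error of 0.0497 at 8% and power of 0.8015 at 12%. So 362 is reproduced.

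**Step 2: one third of HREC metastases missed, prevalence as planned.** The pooled rate found is (2h/3 + l)/2.

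| HREC/LREC (%) | Pooled rate found | Pass probability |
|---|---|---|
| 24/0 | 8.0% | 4% |
| 22/2 | 8.3% | 7% |
| 20/4 | 8.7% | 12% |
| 18/6 | 9.0% | 17% |
| 16/8 | 9.3% | 23% |

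**Step 3: same miss, LREC positivity above plan.** At 20/4, HREC found is 20 × 2/3 = 13.3%.

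| LREC found | True overall prevalence | Pooled rate found | Pass probability |
|---|---|---|---|
| 4% | 12% | 8.7% | 12% |
| 6% | 13% | 9.7% | 30% |
| 8% | 14% | 10.7% | 54% |
| 10% | 15% | 11.7% | 75% |

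Over all five splits, the pass probability is 38% to 68% with LREC 4 points above plan, and 62% to 85% with LREC 6 points above.

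**Step 4: what HREC data alone could show (illustration, HREC 20% against 13.3%).**

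- All 181 HREC women (362/2), reject at 33 or more: error 0.038, power 75%.
- At 20/4 with nothing missed, the trial stops at 150 in 25% of cases (18% success, 7% futility). The chance of continuing and reaching 33 is 55%.
- After closure at 150, an exact one-sided 5% test on 75 women has 43% power.

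**Step 5: how far a fixed limit of 33 depends on the assumed 20%.** With one third missed, 33 of 181 is reached in 3.8% of trials at true HREC prevalence 20%, 23% at 24%, 31% at 25% and 75% at 30%. With nothing missed, it is reached in 50% at 18% and 23% at 16%.

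**The case against.** The strongest reply is that a histologically positive node is real disease, so LREC positivity cannot exceed LREC prevalence. The large figures in Step 3 therefore need overall prevalence of 13% to 15%, not 12%. In part they restate another weakness, a fixed benchmark that may be wrong. This stands. A reader might infer that the pooled rule readily hides a one-third miss even at exactly 50/50 and 12%; Step 2 does not support that.

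Ultrasectioning and immunohistochemistry also apply to every SLN, HREC included, so a rise in LREC alone is an assumption. That stands too. A rise is conceivable, because the LREC aim is more detection and Section 11 does not say whether isolated tumour cells alone count as positive. The documents give no size for it.

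A reader might next propose 33 of 181 HREC women as the replacement rule. Step 5 shows that it shares the dependence on an assumed rate. The only 20% node-positive figure in Section 11 is in the lymphedema paragraph, in a sentence covering both risk groups, and is not labelled as an HREC rate.

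Nor do the documents support saying that LREC has no comparator: Section 1 sets a histology-based expectation for both groups. Section 6.0 mentions sensitivity and negative predictive value, and Section 10 has potential false negatives monitored. But Section 11 attaches no target or HREC analysis to any of these, and under SLN-only surgery misses are largely unseen.

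**Conclusion.** The mismatch between claim and test holds on the text alone: the replacement aim is confined to HREC, while the only rule pools both groups against 8%. A pooled rejection does not by itself support replacement in HREC.

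The size of the masking is conditional. With prevalence as planned and one third of HREC metastases missed, the rule passes in 4% to 23% of trials. It reaches 30% to 75% (20/4 split) only when LREC positivity is 2 to 6 points above the planning figure. These results rest on the inferred cut-off of 38, the assumed splits and an even mix at both stages.

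If complete pelvic lymphadenectomy were in fact done in all HREC women, sensitivity could be measured directly, but Section 11 would still not test it.

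**What to change.** 1. Keep the pooled test, described as an overall detection result. State that rejection, including early rejection at 150, does not alone support replacement in HREC.
2. Base the replacement statement on HREC women only. Report their SLN-positive proportion with a confidence interval against the HREC proportion expected from final histology, the benchmark that Section 1 already names.
3. Fix the HREC definition, expected rate and margin in advance, and show the result over a range of expected rates. The overview counts deep myometrial invasion as high risk, while surgical group 1 takes grade 1–2 tumours whatever the invasion; the analysis needs one stated definition. Do not adopt 33 of 181 as a fixed limit.
4. Report LREC separately as an estimate with a 95% confidence interval.
5. Reconcile the overview (complete pelvic lymphadenectomy) with Section 4.0/5.0 and Appendix 2 (SLN only), because this decides whether HREC misses can be observed.

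The cost is Section 11 wording and one more analysis of data already collected; no extra women are required. The downside is lower precision for the HREC claim, as Step 4 illustrates: power near 75% only if all 181 HREC women are reached, and about 43% on 75 women after early closure.
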